Meta-analyses of 24 published studies reveal that CT and MRI perform equally poorly in the detection of lymph node metastases from prostate cancer [31]. Results of pooled sensitivity and specificity are 42% and 82%, respectively, for CT and 39% and 82%, respectively, for MRI. Thus, the reliance on either CT or MRI may misrepresent the patient's true status regarding nodal metastases, and misdirect the therapeutic strategies offered to the patient [31]. Radionuclide bone scans are commonly used for monitoring bone metastases. However, as bone scans detect tissue remodeling, as opposed to tumor burden, false positives can be caused by inflammation, previous bone injuries, and arthritis, especially in older men [32].

One of the most challenging aspects of clinically managing prostate cancer is the development of suspected or known disease recurrence after initial definitive therapy. Rising PSA after initial definitive therapy is known as biochemical recurrence (BCR) of prostate cancer and may occur in 20-30% of prostate cancer patients before a more definitive diagnosis of metastatic disease can be established by conventional imaging modalities [33-36].

Therefore, new agents that will detect and localize the primary tumor, as well as small metastatic lesions, with high sensitivity and specificity are essential to more accurately diagnose and stage the disease and monitor therapy.

This particular study aims to focus on the detection of metastatic disease or local recurrence early on in prostate cancer patients with biochemical recurrence. This group of prostate cancer patients after definitive local therapy currently have limited imaging options in the United States. The current standard-of-care imaging tests detect local recurrence or metastatic lesions long after when the serum PSA levels become detectable. Also, these imaging tools are not sensitive or

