In summary, the results from the Phase 1 portion of the study showed that PET imaging with ¹⁸F-DCFPyL in patients with prostate cancer is feasible and safe at a radiation dose that is within acceptable limits for diagnostic PET radiotracers [56].

In the Phase 2 portion of the Jl418 study, the diagnostic performance of ¹⁸F-DCFPyL Injection PET/CT imaging to detect areas of local, nodal and/or distant prostate cancer spread was assessed in 25 patients with clinically localized intermediate or higher risk prostate cancer (clinical stage 2: T2b or GS 2: 7 or PSA 2: 10 ng/mL) prior to undergoing radical prostatectomy with pelvic lymph node dissection (PLND). Areas of intra- and extraprostatic tumor spread identified with ¹⁸F-DCFPyL Injection were compared with postop histopathology as the truth standard.

All 25 subjects included in the analysis had at least high-risk PCa based on pre-surgery clinical, laboratory assessments and biopsy-based histology. ¹⁸F-DCFPyL PET/CT imaging was done 1-7 days before surgery. The analysis was performed at the subject level as well as at the individual right, left side lymph node packet levels (n = 50). Eighteen (72%) subjects had Gleason score 4 + 5 = 9 or 5 + 4 = 9, and 13 (52%) subjects were pT3a and 7 (28%) were pT3b based on whole gland histopathology, and seven (28%) subjects were found to have harbored one or more PCa- positive lymph nodes. A median of 13 (range 4-45) lymph nodes was removed at the time of surgery. Notably, two subjects had bilateral lymph node involvement, resulting in a total of 9 positive lymph packets for the entire study cohort. Positive lymph nodes were typically small, with a median diameter of 3 mm (range 1-12).

Following independent image reads and adjudications, 7 (28%) subjects were confirmed to have 2: 1 site of focal radiotracer within the pelvis consistent with N1 disease. This resulted in a sensitivity and specificity of 71.4% (95% CI 29.0-96.3) and 88.9% (65.3-98.6), respectively, for the presence or absence of metastatic prostate cancer. Similar results were found in the packet-level analysis with a sensitivity of 66.7% (29.9-92.5) and a specificity of 92.7% (80.1-98.5), in good agreement with published ⁶⁸Ga PSMA imaging data [50]. Additionally, the readers determined that 3 (12%) subjects had PET/CT findings consistent with Mla disease (none had Mlb or Mlc). All 3 of these patients had a detectable PSA level within 6 months of surgery.

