- 3. Bone lesions will be considered positive if the uptake is focal and greater than normal marrow uptake.
- 4. Prostate bed and prostate lesions will be considered positive if uptake is focal and greater than background activity of the prostate.

Follow-up imaging:

A chart review will be performed at 3, 6, 9 and 12 months with a plan to communicate with the referring oncologist team regarding the plan for follow-up imaging with a CT, MRI and/or bone scan. If a follow-up imaging is not obtained by 12 months, then imaging will be requested. Interpretation of follow-up imaging will be performed by local read. The follow-up conventional imaging should be the same modality/modalities as the initial staging work-up to allow for reproducible and accurate comparisons.

PET positive findings will be validated as true or false positive as outlined in more detail below. False negative ¹⁸F-DCFPyL PET findings cannot be determined as this would require biopsies of all PET negative lesions that are present on conventional imaging.

¹⁸F-DCFPyL PET validation will be based on follow-up imaging:

- 1. Lymph nodes will be assessed by change in size. PET positive lymph nodes will be considered:
 - a. True positive:
 - If on follow-up imaging within 3-12 months, lymph nodes seen on CT or MRI scan decrease by more than 30% (for patients undergoing systemic treatment of focal therapy at this site) or increase by more than 20% in short axis diameter (with a minimum of 3 mm in change in size).
 - If patients with solitary lymph node regions show a decrease of PSA by greater than 50% after targeted treatment (i.e. external beam radiation) and the lymph nodes do not change in size (less than 30% decrease or less than 20% increase in short axis diameter).

b. False positive:

• If on follow-up imaging within 3-12 months, sites of initial ¹⁸F-DCFPyL PET positive lymph node lesions seen on CT or MRI scan decrease by more than 30% without systemic therapy or focal therapy at this site.

- If PET positive lymph node lesions do not meet the criteria for above false positive or true positive findings.
- 2. Visceral lesions (non-lymph node soft tissue or organ) will be assessed by change in size. PET positive visceral lesions will be considered:
 - a. True positive:
 - If on follow-up imaging within 3-12 months, visceral lesions seen on CT or MRI scan decrease by 30% (for patients undergoing systemic treatment of focal therapy at this site) or increase by 20% in largest diameter.

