 - If patients with solitary visceral metastasis show a decrease of PSA by greater than 50% after targeted treatment (i.e. external beam radiation) and lesions do not change in size (less than 30% decrease or 20% increase in largest diameter).

b. False positive:

- If on follow-up imaging within 3-12 months, sites of initial PET positive lesions seen on CT or MRI scan decrease by more than 30% without systemic therapy or focal therapy at this site.
- If ¹⁸F-DCFPyL PET positive lesions do not meet the criteria for above false positive or true positive findings.
- 3. ¹⁸F-DCFPyL PET positive bone lesions will be considered:
 - a. True positive:
 - If there was a corresponding positive sclerotic lesion on the CT portion of the ¹⁸F-DCFPyL PET in the same location as the focal uptake.
 - If there is focal uptake seen on the baseline bone scan performed within one month of ¹⁸F-DCFPyL PET.
 - If there is a lesion noted on the initial MRI imaging scan performed within one month of ¹⁸F-DCFPyL PET.
 - If within 12 months follow-up CT scan demonstrates development of sclerosis.
 - If within 12 months follow-up MRI scan demonstrates a new bone lesion.
 - If within 12 months follow-up bone scan demonstrates new focal uptake.

b. False positive:

- If ¹⁸F-DCFPyL PET positive bone lesions do not meet the criteria for true positive findings.
- 4. ¹⁸F-DCFPyL PET positive prostate bed and prostate lesions will be considered:
 - a. True positive:
 - If on follow-up imaging within 12 months, lesions seen on CT or MRI scan decrease by 30% (for patients undergoing systemic treatment of focal therapy at this site) or increase by 20% in largest diameter.

• If patients with prostate bed lesions show a decrease of PSA by greater than 50% after targeted treatment (i.e. external beam radiation) and lesions do not change in size (less than 30% decrease or 20% increase in largest diameter).

b. False positive:

- If on follow-up imaging within 3-12 months, sites of initial ¹⁸F-DCFPyL PET positive lesions seen on CT or **MRI** scan decrease by more than 30% without systemic therapy or focal therapy at this site.
- If ¹⁸F-DCFPyL PET positive lesions do not meet the criteria for above false positive or true positive findings.

Histopathology/Biopsy:

- 1. Localization of lesions for histopathology/biopsy will be classified according to the regions in table (Definition of regions) below.

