3.10 STATISTICAL METHODS PLANNED IN THE PROTOCOL AND DETERMINATION OF SAMPLE SIZE

3.10.1 Study Design

This is a single arm phase II clinical trial to evaluate the positive predictive value (PPV) of ¹⁸F-DCFPyL PET imaging in men diagnosed with prostate cancer with increasing prostate-specific antigen (PSA) levels. PPV is the number of true positives (TP) divided by number of patients who are tested positive (i.e., TP + FP) based on the PET imaging. The determination of TP and positive testing is detailed in Section 3.5.1. Secondary endpoints are PPV of ¹⁸F-DCFPyL PET (per-region). All patients who are diagnosed with prostate cancer with increasing PSA levels and who have received PET scans will be evaluable for the analysis.

All patients will be followed up for histopathologic analysis, conventional imaging (CT, MRI and/or bone scan) and/or serum PSA after focal salvage therapy acquired during clinical routine. Combination of (in descending priority) histopathologic analysis, imaging, and PSA follow-up after local/focal therapy will used for lesion validation. Validation will be performed by the unblinded local investigators after reviewing images and reports, following prespecified criteria of the study protocol. In patients with follow-up, positive ¹⁸F-DCFPyL PET findings will be validated as true or false-positive results. Region negative on ¹⁸F-DCFPyL PET, but with subsequently confirmed prostate cancer by histopathologic analysis, will be considered false-negative results. True negative will not be defined. (please see section 3.5.1. for details).

3.10.2 Sample Size

A total of 300 evaluable participants will be enrolled into this study. We expect approximately 85% of them, i.e., 255 patients, will have positive test results. Based on these 255 patients, the exact 95% confidence interval (CI) for PPV has a width ofless than 12%. The following table shows the exact 95% CI corresponding to different observed PPV values.

Observed PPV	95% CI of true underlying PPV
80%	(75%, 85%)
84%	(79%, 88%)
88%	(84%, 92%)
92%	(88%, 95%)
96%	(93%, 98%)
100%	(99%, 100%)

As an example, from this table, an observed 80% PPV value indicates that we can be 95% confident that the true underlying PPV lies in the interval (75%, 85%). If the observed PPV is 88%, then we can be 95% confident that the true underlying PPV lies in the interval (84%, 92%).

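### Soft-tissue PET foci with no measurable baseline have no new-lesion route to true positive, so a lesion that later appears at the PET site falls into the false-positive catch-all

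*Combined protocol and SAP*

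**What the plan says.** Section 3.5.1 sets out how PET-positive lesions are validated on follow-up imaging, in four lists.

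- **Nodes (item 1).** A lesion is true positive if it shrinks by more than 30% under treatment, or on "increase by more than 20% in short axis diameter (with a minimum of 3 mm in change in size". The window is 3-12 months.
- **Visceral lesions (item 2).** A 30% decrease under treatment or a 20% increase in largest diameter, in the same window.
- **Prostate and prostate bed (item 4).** A 30% decrease under treatment or "increase by 20% in largest diameter". Here the true-positive window is within 12 months.
- **Bone (item 3).** No size measurement is used. Besides findings at baseline, three later events confirm the lesion: sclerosis developing on CT, new uptake on bone scan, and "If within 12 months follow-up MRI scan demonstrates a new bone lesion".

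Items 1, 2 and 4 also have a PSA route, which needs targeted treatment, a PSA fall above 50% and a lesion that has not changed in size. Their false-positive rules are a decrease above 30% without treatment, followed by a catch-all. The nodal catch-all is "If PET positive lymph node lesions do not meet the criteria for above false positive or true positive findings", and items 2 and 4 carry the same rule.

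Section 3.10.1 ranks histopathology above imaging and imaging above PSA, and assigns validation to unblinded local investigators who apply the prespecified criteria.

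**The concern.** A percentage increase needs a starting diameter. A PET-positive soft-tissue focus that could not be measured on CT or MRI at the time of PET has none. If a lesion becomes visible at exactly that place on follow-up, this is strong imaging evidence that the PET was right. Yet the growth rule cannot be computed, the shrinkage rules do not apply, and the PSA route assumes no change in size. Only the catch-all remains, and it counts the lesion against the tracer.

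The bone list accepts later appearance as confirmation, so the protocol endorses the principle but writes it for Region 4 only. At stake are the secondary endpoint (PPV in Regions 1-3) and the primary per-patient PPV in men with no other confirmed lesion. The direction is known: PPV is understated. If validators instead supply their own baseline value, the classification rests on unblinded judgement and not on a written rule.

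**Working it through.** **Step 1: set the rules side by side.** Take a PET-positive focus that is not measurable at baseline, a lesion at the same site on follow-up CT or MRI, and no decisive histology.

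| Route in 3.5.1 | Nodes, visceral, prostate bed | Bone |
|---|---|---|
| Growth by percentage | Not computable | Not used |
| Decrease under treatment | Not met | Not used |
| New appearance | No rule | True positive |
| PSA fall with unchanged size | Does not clearly fit a new lesion | Not used |
| Decrease without treatment (false positive) | Not met | Not used |
| Catch-all | False positive | Not reached |

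**Step 2: the percentage.** Change = (follow-up - baseline) / baseline. A node going from 5 to 8 mm gives (8 - 5)/5 = 60% with a 3 mm change, so it is true positive. From no measurable baseline to 8 mm gives (8 - 0)/0, which is undefined. The 3 mm minimum is an added condition for nodes, not an alternative to the percentage. Items 2 and 4 have no such minimum.

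**Step 3: reproduce the plan's precision table.** Section 3.10.2 states: "A total of 300 evaluable participants will be enrolled into this study". It continues: "We expect approximately 85% of them, i.e., 255 patients, will have positive test results". So 300 x 0.85 = 255. Exact (Clopper-Pearson) 95% limits for x of n use the beta quantiles B(0.025; x, n-x+1) and B(0.975; x+1, n-x):

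| x/255 | PPV | Exact 95% CI | Plan's table |
|---|---|---|---|
| 204 | 80.0% | 74.6-84.7 | 75-85 |
| 214 | 83.9% | 78.8-88.2 | 79-88 |
| 225 | 88.2% | 83.6-91.9 | 84-92 |
| 235 | 92.2% | 88.1-95.1 | 88-95 |
| 245 | 96.1% | 92.9-98.1 | 93-98 |
| 255 | 100% | 98.6-100 | 99-100 |

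The table reproduces. The 88% row needs the count rounded up to 225; with 224 the interval is 83.2-91.6. The widest interval is 10.2 points, inside the stated 12.

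**Step 4: how many men would matter.** The documents give no frequency, so the number of men moved (m) is an assumption. Start from 224/255 = 87.8%, taken as the PPV with a new-lesion rule, and move m men from true to false positive:

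| m (share of 255) | PPV | Exact 95% CI | Contains 87.8%? |
|---|---|---|---|
| 0 | 87.8% | 83.2-91.6 | yes |
| 5 (2.0%) | 219/255 = 85.9% | 81.0-89.9 | yes |
| 12 (4.7%) | 212/255 = 83.1% | 78.0-87.5 | no |
| 13 (5.1%) | 211/255 = 82.7% | 77.5-87.2 | no |

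Twelve is the smallest m for which the reported interval excludes the starting PPV. The corresponding number is 14 men (5.5%) from 204/255 and 10 men (3.9%) from 235/255. These are thresholds, not estimates of what will happen.

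**The case against.** **A validator may read going from invisible to visible as growth above 20%.** For nodes, the 3 mm minimum could even serve as the working test. This is a reasonable reading, and it means the misclassification is not certain in every case. But the text does not say it, items 2 and 4 have no minimum, and the validators are unblinded. The objection turns a definite error into an unwritten judgement, which still needs a sentence.

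**A reader might take a large loss of PPV from the background section.** Section 1.2 reports "Results of pooled sensitivity and specificity are 42% and 82%, respectively, for CT and 39% and 82%, respectively, for MRI", which invites the inference that about 58-61% of node-positive men have no conventional correlate. That does not follow. The same section says CT and MRI depend on enlargement, with lesions above 1 cm, so a node missed on size criteria may still be visible and measurable. The sensitivities are not conditional on a positive PET, and they say nothing about visceral or prostate-bed lesions. The J1418 summary in section 1.6.1 adds "Positive lymph nodes were typically small, with a median diameter of 3 mm (range 1-12", but that covers all positive nodes, including those in packets that PET missed. Eligibility does not require negative conventional imaging.

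**A reader might also say the comparison between regions is distorted.** No such comparison is planned. Section 3.10.3 reports separate percentages with exact intervals.

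**The reach is limited.** Histology outranks imaging and is sought when feasible, and per-patient PPV moves only if no other lesion is confirmed. Both limits stand. They narrow the effect without removing it.

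**Conclusion.** The gap is real and should be closed. Read literally, section 3.5.1 makes a newly visible soft-tissue lesion at a PET-positive site a false positive when there was no measurable baseline and no decisive histology. For bone, the same event is a true positive. The bias is downward, directly on PPV for Regions 1-3 and on per-patient PPV only in men without another confirmed lesion.

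Its size is unknown. No PPV loss can be derived from the documents, and the CT and MRI sensitivities in section 1.2 do not supply the missing frequency. What can be said is that the margin is narrow: at 224/255, 12 men (an assumed 4.7%) would be enough for the reported interval to exclude the PPV that a new-lesion rule would give, while 5 men would not. Estimating PPV with that precision is the only justification given for the sample size, so a classification gap that could matter at this level is worth removing.

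**What to change.** Add one true-positive bullet to each of items 1, 2 and 4 in section 3.5.1, using that item's own follow-up window (3-12 months for items 1 and 2, within 12 months for item 4). Suggested text: *a new lesion on follow-up CT or MRI at the same anatomic site as a PET-positive focus that had no measurable correlate on CT or MRI at the time of PET.* For nodes, apply the existing 3 mm minimum with the unseen baseline taken as 0 mm. State that the catch-all does not apply to these lesions. Flag them on the validation form, and report PPV a second time with them counted as false positive.

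The cost is three bullets, one sentence on the catch-all, one data field and one sensitivity analysis. It needs no extra scan, reader or patient. The downside is that a benign or reactive lesion that becomes visible at the site could be counted as true positive. Reporting PPV both ways shows how far the result depends on these cases.

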To determine the positive predictive value (PPV) of ¹⁸F-DCFPyL Positron Emission Tomography (PET) on a per-patient basis in men diagnosed with prostate cancer with increasing PSA levels.

Secondary Objective:

To determine the PPV of ¹⁸F-DCFPyL PET on a per-region basis, specifically focusing on the prostate or prostate bed, pelvis, extra pelvis, and bones.

ENDPOINTS

Primary Endpoint:

Positive predictive value (PPV) of ¹⁸F-DCFPyL PET (per-patient): Number of true positives (TP) divided by number of TP plus number of false positives (FP) as detailed in Section 3.5.1.

Secondary Endpoint:

Positive predictive value (PPV) of ¹⁸F-DCFPyL PET (per-region): TP/TP + FP as detailed in Section 3.5.1.

Name of Sponsor	[name]	
Investigational Product	¹⁸ F-DCFPyL	
METHODOLOG	GY TO THE PROPERTY OF THE PROP	
Study Design	This is an interventional, single group assignment, prospective non-randomized, open label Phase 2 trial designed to evaluate the PPV of ¹⁸ F-DCFPyL PET imaging in men diagnosed with prostate cancer with increasing prostate-specific antigen (PSA) levels. Eligible patients will undergo baseline assessments as per the Schedule of Study Activities in Appendix A. A schematic of the study design can be found in Appendix B. Approximately 300 participants are planned for enrollment in this study. Participants will receive a single dose of ¹⁸ F-DCFPyL and undergo a PET imaging study. The PET imaging maybe repeated at a later date if the biopsy of the lesion is negative and if the lesion is present on follow-up imaging.	
Intervention	The intervention is a PET CT scan with a single dose of the radiolabeled prostate-specific membrane antigen (PSMA) ligand, ¹⁸ F-DCFPyL. ¹⁸ F-DCFPyL PET will be acquired using a GE Discovery PET-CT scanner.	
Intervention Duration	Patients meeting study eligibility criteria will receive one dose of ¹⁸ F-DCFPyL supplied by the current Good Manufacturing Practice (cGMP)-compliant PET production facility and will be monitored for safety for 120 minutes following administration.	
Investigational Agent and Formulation	¹⁸ F-DCFPyL Injection is an ¹⁸ F-labeled small molecule that targets the extracellular domain of PSMA. It is a sterile, clear particle-free solution supplied at a specific activity of at least 1000 mCi/μmol at the Time of Administration (TOA), and a radioactivity concentration (RAC) of 1-90 mCi/mL at the Time of Calibration (TOC).	

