- 2. The ¹⁸F-DCFPyL PET positive findings will be targeted to be confirmed by histopathology/biopsy if and whenever clinically feasible.
- 3. Histopathological procedures, biopsies and follow-up imaging will be performed as clinically indicated and as per the standard of care/institutional protocol. The following elective procedures may guide the investigator:
 - A. Positive HP/Biopsy: Confirmed sites of metastatic or tumor involvement by histopathology/biopsy will be discussed with the responsible physician/surgeon.
 - B. Negative Biopsy: Patients with suspected tumor recurrence on the PET with negative histopathology/biopsy will be handled as outlined below:

1. Lymph nodes:

- For patients undergoing nodal dissection: Patients will be rescanned with dedicated CT or MRI scan, if clinically feasible, to determine if the suspicious ¹⁸F-DCFPvL PET positive node was removed.
 - o If PET positive lymph node is still present, a repeat biopsy can be pursued if clinically feasible and applicable, or follow-up using imaging as described above will be performed.
 - o If the corresponding node was removed, then this will be considered a False Positive.
- For patients undergoing needle biopsy: Images of the procedure will be reviewed to determine if the correct node was biopsied.
 - o If the correct node was biopsied, then a negative biopsy will be considered a False Positive.
 - o If the incorrect node was biopsied, then follow-up imaging as described above will be performed if clinically feasible.

- 11. Bone lesions: Given the high rate of false negative biopsies for osseous metastases in patients with prostate cancer, patients with negative bone biopsies of PET positive lesions will be further evaluated:
 - If pathology demonstrates alternative diagnoses that is known to be PET positive (e.g. Renal Cell Carcinoma metastases, Paget's disease), then this will be considered a False Positive.
 - If pathology is indeterminate, then follow-up imaging as described above will be performed to determine if the lesion is a True Positive or False Positive.
- Additionally, a repeat ¹⁸F-DCFPyL PET may also be obtained as per treating physician discretion in addition to repeat conventional imaging (CT and/or MRI) in cases of negative biopsy to determine if the biopsy was true negative or false negative.
- C. Although not routinely performed during standard practice, immunohistochemical or specimens (primary and lymph node metastases) may be performed, although not required.

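### Section 3.5.1 lets a repeat DCFPyL PET re-judge a negative biopsy with no scoring rule, and lets same-session CT alone confirm a bone lesion; PPV is not reported by source of verification

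*Combined protocol and SAP*

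**What the plan says.** PPV is the only efficacy endpoint: per patient (primary) and per region (secondary). The TP and FP rules in section 3.5.1 therefore define the endpoint.

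- **Reference standard.** The synopsis (Statistical Methods, Efficacy) and section 3.10.1 rank histology first, then imaging, then PSA after local therapy. Both name the follow-up imaging as conventional: CT, MRI and/or bone scan. Unblinded local investigators validate against prespecified criteria.
- **Bone lesions.** The criteria are introduced with "PET validation will be based on follow-up imaging". The first bone TP criterion is a "corresponding positive sclerotic lesion on the CT portion of the" index PET, at the site of uptake. The others are a baseline bone scan or MRI within one month, and new findings on CT, MRI or bone scan within 12 months. Any one suffices. A lesion is FP if "PET positive bone lesions do not meet the criteria for true positive findings".
- **Negative biopsy.** For needle biopsy of nodes: "If the correct node was biopsied, then a negative biopsy will be considered a False Positive". For bone: "patients with negative bone biopsies of PET positive lesions will be further evaluated", with outcomes given for an alternative diagnosis and for indeterminate pathology. A further bullet allows a repeat DCFPyL PET at the treating physician's discretion, alongside repeat CT and/or MRI, "in cases of negative biopsy to determine if the biopsy was true negative or false negative".
- **Repeat scan elsewhere.** In the synopsis and section 3.1.1 the PET "maybe repeated at a later date if the biopsy of the lesion is negative and if the lesion is present on follow-up imaging".
- **Analysis.** Section 3.10.3 plans PPV per patient and per region with exact 95% CIs, and no breakdown by source of verification.

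**The concern.** PPV asks how often a positive scan is confirmed by something other than that scan. Two routes in section 3.5.1 weaken this separation. The repeat PET uses the same tracer to decide whether a negative biopsy should be believed, although biopsy is the top-ranked reference. The CT route takes confirmation from the same imaging session.

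Both can feed the primary PPV and the bone-region PPV. The validators are unblinded and are told to follow prespecified criteria, but none exists for a repeat PET. With no breakdown by source, a reader of the results could not tell how much of the PPV rests on evidence independent of the index scan.

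**Working it through.** **1. The plan's own figures.** Section 3.10.2 expects 85% of 300 participants to be PET-positive: 300 × 0.85 = 255. Exact (Clopper-Pearson) 95% limits at n=255 are 74.6–84.7% for 204/255 (80.0%) and 83.6–91.9% for 225/255 (88.2%). These match the tabulated 75–85% and 84–92%, so 255 is the denominator used below.

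**2. The repeat-PET bullet set beside the other rules.**
- *Priority order (synopsis, 3.10.1).* Histology ranks first. The bullet lets another scan judge whether a histology result is false.
- *Type of imaging (same places).* Follow-up imaging is CT, MRI and/or bone scan. A DCFPyL PET is none of these and has no stated rank.
- *Scoring criteria (3.5.1).* They use size, sclerosis, bone-scan or MRI findings, and PSA. None uses repeat tracer uptake, and nothing says what prevails if a repeat PET disagrees with biopsy, CT or MRI.
- *Node rule (3.5.1).* A correctly targeted negative needle biopsy is already FP. The text does not say whether the bullet can reopen it.
- *Condition on rescanning (synopsis, 3.1.1).* The lesion must be present on follow-up imaging. The bullet refers to physician discretion and does not repeat that condition. The two can be read together, so this is a possible tension only.
- *Remaining bone biopsies (3.5.1).* For a negative result that is neither an alternative diagnosis nor indeterminate, the text does not say whether histology decides or the bone criteria and their FP default apply.

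Direction: a repeat PET could push a lesion towards TP or towards FP. With no scoring rule, the direction of any bias is undetermined.

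**3. The CT route.** Bone positivity in 3.5.1 is focal uptake above normal marrow. Sclerosis is a separate anatomic sign, so confirmation is not fully circular, although it comes from the index session. The criterion can turn an otherwise FP lesion into a TP and never the reverse, so any error in it raises PPV.

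**4. Scale.** The documents do not give the number of patients whose TP status rests solely on one of these routes. They also state no lesion-to-patient rule for TP. I assume that one TP lesion makes the patient TP, so a patient with another TP lesion changes nothing.
- One patient re-scored from TP to FP: 1/255 = 0.39 points.
- One patient excluded instead: (1 − PPV)/(n − 1). From 224/255 (87.84%) this gives 223/254 = 87.80%, a change of 0.05 points.

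For k such patients, starting from 224/255 = 87.8% (exact CI 83.2–91.6%), scoring as FP gives (224 − k)/255 and exclusion gives (224 − k)/(255 − k). The values of k are assumed, only to show how the two treatments differ:
- k=5 (2% of 255): FP 219/255 = 85.9% (81.0–89.9); excluded 219/250 = 87.6% (82.9–91.4).
- k=10 (4%): FP 214/255 = 83.9% (78.8–88.2); excluded 214/245 = 87.3% (82.5–91.2).
- k=26 (10%): FP 198/255 = 77.6% (72.0–82.6); excluded 198/229 = 86.5% (81.3–90.6).

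For the bone region no denominator is given. Over an assumed 25 to 100 PET-positive bone regions, one region re-scored as FP moves PPV by 1/25 = 4.0 to 1/100 = 1.0 points.

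**The case against.** The strongest reply is that the rest of the plan already contains the repeat PET. Follow-up imaging is named as conventional, no TP criterion uses repeat uptake, and a lesion meeting no criterion is FP. The biopsy steps are offered as elective guidance, and the repeat PET is optional and additional to CT or MRI. On that reading a repeat PET cannot by itself create a TP. This largely stands: incorporation of the index test into its own reference standard is permitted by the wording of one bullet, not established. What survives is that the bullet states a purpose which, taken literally, conflicts with those other rules.

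On CT, the reply is that the criterion was chosen in advance and rests on a sign other than uptake. That stands too. The mismatch with the follow-up-imaging lead-in is weak, because the list beneath it also contains baseline bone scan, baseline MRI and PSA. Section 3.8.2 describes the session CT as low dose, for attenuation correction and co-registration, while Appendix A note f calls for dedicated follow-up imaging. A reader might infer that sclerosis is misread on the session CT; nothing in the documents shows that.

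The missing breakdown by source contradicts nothing in the plan, since section 3.10.3 analyses the stated endpoints. It is a cheap improvement.

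**Conclusion.** The point holds as an inconsistency in the reference-standard rules plus a gap in reporting. The severity is between minor and should-fix. The repeat-PET bullet needs reconciling; the CT criterion can stay, provided its contribution is visible.

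Three stronger conclusions are tempting and unsupported:
- *That PPV will be inflated.* Only the CT route has a known direction. The repeat-PET route and the net effect do not.
- *That the effect is material.* No affected count is given, so the size cannot be derived. Each patient moves PPV by at most 0.39 points at n=255.
- *That re-scoring 9 to 14 patients would be decisive because PPV would then fall below its original lower limit.* For PPVs of 96% down to 80% the arithmetic is right, but it largely restates the half-width of the CI, and section 3.10.2 sets no decision threshold. Exclusion moves PPV far less: removing 14 from 204/255 gives 190/241 = 78.8%, against 80.0%.

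These figures assume 255 PET-positive patients and that one TP lesion makes a patient TP.

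**What to change.** 1. In section 3.5.1, state that DCFPyL uptake, initial or repeat, does not determine TP or FP status, so that after a negative biopsy only histology and the existing conventional-imaging and PSA criteria count. Reconcile the repeat-PET bullet with the condition in the synopsis and section 3.1.1, with the node-biopsy rule and with the priority order. State which existing rule governs the remaining negative bone biopsies. Whether to rescan stays a care decision.
2. Keep the bone criteria, including CT sclerosis, in the primary definition. Record the source of verification for each lesion when it is validated, and in section 3.10.3 report PPV by source: histology, follow-up imaging, same-session CT only, other baseline imaging, PSA.
3. Add a sensitivity analysis for bone lesions that are TP only by same-session CT, done two ways: scored FP with the denominator unchanged, labelled a worst-case bound; and excluded as not independently verified. Note beside the first that the follow-up CT criterion requires sclerosis to develop. A lesion already sclerotic at baseline cannot readily meet it and may become FP by construction.

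Cost: wording in sections 3.5.1 and 3.10.3, one recorded field and one table, with no new procedures or visits. The downside is that PPV may be lower in the sensitivity analysis.
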